### 5.5 Secondary Safety Outcome Variables

Secondary safety outcome variables: Blood safety parameters: Creatinin, Potassium, Sodium, ALAT, ASAT, HbA1c, Glucose (from HbA1c), CRP, Leucocytes, Thrombocytes

Each parameter will be analysed using a proc mixed model with patient as Random effect.

Sequence and period effect will be evaluated prior evaluating the treatment effect in a similar way as the primary efficacy outcome variable.

For statistical analysis of data measured on an interval scale model check is assessed using QQ residual plots together with Kolmogorov-Smirnov test for normality.

In case for normality not reached using untransformed data nor transformed data using the log2-scale, appropriate non-parametric statistical methods will be used instead.

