Chronic, low-dose use (commonly defined as 75–325 mg daily) of ASA is widely recommended for both primary and secondary prevention of CVD. More than 30% of the US population aged above 40 years are estimated to be taking chronic, daily, low-dose ASA for that reason alone. However, chronic use of ASA is also associated with adverse effects, including small-intestinal mucosal lesions and ulcers, perforations, major hemorrhage, and, in rare instances, death. A recent review and meta-analysis addressing both the efficacy of ASA in prevention of CVD and also bleeding-related adverse effects concluded that a balanced, cautious approach should be taken in the case of primary CVD prevention because of these adverse effects, highlighting the unmet need to reduce the risk of adverse effects associated with chronic ASA use. The present trial is part of a larger clinical program by the sponsor aiming at bringing a dietary solution to the marked that can help chronic ASA users with these side-effects. As such, the investigators and sponsor believe that the potential benefits the trial results will bring outweigh the mild discomfort that the healthy volunteers enrolled in this trial may experience.

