A non-fasting blood sample will be collected from all participants at all 5 visits for safety reasons and in order to detect any unknown condition that may compromise a participant's eligibility for the study. The parameters include creatinine, potassium, sodium, haemoglobin, haematocrit, red blood cells, HbA1c, alanine aminotransferase, aspartate transaminase, INR, leucocytes, thrombocytes and CRP.

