### 5.6 Secondary Efficacy Outcome Variables

Secondary Efficacy outcome variables: Erythrocytes, Haematocrit, Haemoglobin, INR. All variables are analysed like the secondary safety outcome variable analysis.

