### 5.7 Sensitivity analysis on secondary variables

Percent change from baseline on the above secondary variables will also be analysed, where baseline value prior each period (visit 2 and visit 4) is set to index=100.

Subject 1, visit 2 = 1.2 (index=100)

Subject 1, visit 3 = 3.4 (index=283.3, calculated as  $100*3.4/1.2$ )

Subject 1, visit 4 = 2.3 (index=100)

Subject 1, visit 5 = 1.0 (index=43.5, calculated as  $100*1.0/2.3$ )

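### The SAP analyses the safety blood panel only by group-level tests, which are practically insensitive to a large change in one to three of about 20 subjects, and it plans no output showing individuals

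*SAP*

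**What the plan says.** Protocol 6.6.2 has the blood panel drawn at all five visits "for safety reasons and in order to detect any unknown condition that may compromise a participant's eligibility for the study". Protocol 5.2 lists the harms of the challenge drug: "chronic use of ASA is also associated with adverse effects, including small-intestinal mucosal lesions and ulcers, perforations, major hemorrhage".

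The SAP handles the panel as follows:

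- **5.5 (ten safety parameters):** "Each parameter will be analysed using a proc mixed model with patient as Random effect". Residuals are checked with QQ plots and a Kolmogorov-Smirnov test. If neither the raw nor the log2 scale is normal, "appropriate non-parametric statistical methods will be used instead".
- **5.6 (four parameters, including those most likely to reflect bleeding):** "Secondary Efficacy outcome variables: Erythrocytes, Haematocrit, Haemoglobin, INR", and "All variables are analysed like the secondary safety outcome variable analysis".
- **5.7:** "Percent change from baseline on the above secondary variables will also be analysed".
- **5.9:** a before/after comparison over both periods, with a similar model.

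The SAP contains no shift table, out-of-range count, largest-change summary, individual listing or adverse-event table. SAP 5.12 promises descriptive reporting of disposition, demographics and other characteristics, but does not name laboratory values. A Safety Analysis Set appears among the abbreviations, but section 4 does not define one.

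**The concern.** Ulceration, perforation and haemorrhage happen to individuals. A panel drawn for safety should therefore let the reader see whether any individual changed markedly. Every planned analysis estimates or tests an average or overall shift instead.

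The treatment contrast has a second limitation. Subjects take 300 mg ASA in both periods, so Bif195 minus placebo compares two aspirin conditions. A subject whose haemoglobin falls equally in both periods cancels out of it. Only the before/after model in SAP 5.9 addresses aspirin, and it averages one affected subject-period with about 39 others.

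At stake is the content of the report. Following the SAP as written, it could show no significant effect on haemoglobin, creatinine or ALAT, and contain no table from which a reader could learn that one subject had a large change.

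**Working it through.** **Inputs from the documents.** 20 completers (Protocol 6.9.8), two periods per subject (Protocol 6.2), two-sided 5% level (SAP 5.1). The documents give no laboratory SD and no size of fall, so those below are assumptions.

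**The plan's own figure.** The only power statement (Protocol 6.9.8) concerns gene expression: n = 20 gives power 0.95 for a 1.5-fold change with CV 0.344. A negative-binomial formula reproduces it: n = 2(1.960 + 1.645)² × (1/depth + 0.344²) / (ln 1.5)². This gives 18.7 at unlimited read depth and 20.0 at a depth of about 122; 20/(1 − 0.2) = 25 randomised. It says nothing about the laboratory analyses.

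**Step 1: a limit that needs no SD.** Let m of N subjects fall by D in one treatment period. As D grows, the paired t statistic tends in size to

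t = (m/N) / √[ m(1 − m/N) / ((N − 1)N) ].

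For N = 20, m = 1: 0.05 / √(0.95/380) = 0.05/0.05 = 1.00.

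| Affected of 20 | Limiting t | p |
|---|---|---|
| 1 | 1.00 | 0.33 |
| 2 | 1.45 | 0.16 |
| 3 | 1.83 | 0.083 |
| 4 | 2.18 | 0.042 |

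The outlying fall moves the mean but inflates the variance as well. Treating SAP 5.9 as 40 before/after pairs gives almost the same limits: 1.00, 1.43, 1.78 and 2.08.

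**Step 2: a worked size.** One subject of 20 falls 30 g/L in one period. The mean contrast moves by 30/20 = 1.5 g/L. With an assumed SD of 5 g/L for a subject's per-period change, the expected variance of the paired difference is 2 × 5² + 30² × 0.95/19 = 50 + 45 = 95. The standard error is √(95/20) = 2.18, so t is about 1.5/2.18 = 0.69.

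**Step 3: simulated rejection rates** (20,000 trials per setting, plain paired t test, two-sided p < 0.05).

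| Setting | SD 4 | SD 5 | SD 7 |
|---|---|---|---|
| Treatment contrast, one fall of 20 g/L | 4.3% | 4.5% | 4.8% |
| Treatment contrast, one fall of 30 g/L | 3.2% | 3.8% | 4.6% |
| Treatment contrast, two falls of 30 g/L | 6.8% | 8.2% | 8.5% |
| Before/after mean, one fall of 30 g/L | 3.1% | 4.0% | 4.6% |

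Over falls from 0 to 20 SD, the rate for two affected subjects peaks at about 8% and for three at about 18% (near 8 SD). With four it rises throughout, to 61% at 20 SD. A subject falling equally in both periods leaves the treatment test at 5%.

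**Step 4: closer to the SAP's procedure.** A fitted mixed model (300 runs; treatment, sequence, period, Visit 2 baseline, random subject) with one affected subject rejects in 7.0% of runs with no fall, 3.0% at 6 SD and 0.3% at 10 SD. A normality test followed by a signed-rank fallback (1,500 runs, without the log2 step) gives 5.6% with no fall, 4.1% at 10 SD and 3.5% at 15 SD, where the fallback is used in 90% of runs.

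**The case against.** **Individual harm has other routes.** This stands as far as conduct goes. Protocol 6.8.1 has the panel analysed in-house on the day of collection. Protocol 6.10.1 counts abnormal laboratory findings as adverse events, each with follow-up, intensity and causality. Four gastroscopies record haemorrhages, erosions and ulcers. A reader might infer that a bleeding subject would go unnoticed; the documents do not support that. But the protocol sets no laboratory criterion for an adverse event, 6.10.2 elicits events by asking what the subject has noticed, gastroscopy sees only stomach and duodenum, and the SAP tabulates no adverse events. The gap is in planned reporting.

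**The t test ignores the normality check and fallback.** This stands as a limit on the simulation. The fallback largely flattens any decline in detection, and a QQ plot would often expose the outlier to the analyst. Neither is a safety output, and detection with one affected subject stays near 5%.

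**The tempting stronger reading** is that the test becomes less likely to flag harm the larger the fall. That should not be claimed. The two-sided rates mix rejections in both directions. Counting only the harm direction, a separate run gave 2.5% with no fall and 3.0%, 3.9% and 4.4% with one 30 g/L fall at SD 4, 5 and 7. At SD 7 the harm-direction rate does not decline between 20 and 30 g/L (4.3% and 4.4%). With two or three affected subjects detection rises before it falls, and with four it rises throughout. A steep decline at very large falls arises when the SAP's own normality check is left out.

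**The trial does not aim to measure aspirin harm.** True: the objective is mechanistic. The haemorrhage sentence concerns chronic use, whereas this is 28 days per period in healthy adults aged 18 to 40 with ulcer history and bleeding disorders excluded. That lowers the chance of a case, but the panel is still drawn for safety.

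**Conclusion.** The point holds in this form: the SAP's laboratory analysis is group-level throughout, practically insensitive to a large change in one to three of about 20 subjects, and accompanied by no individual-level output. With one affected subject, p < 0.05 occurs at about the false-positive rate or less. With two it occurs in at most about 8% to 9% of trials, and with three in at most about 18%.

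The limiting t values depend only on the numbers of subjects. The percentages rest on assumed SDs and falls, normal errors and mostly a plain paired t test.

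No passage says that non-significant contrasts will be presented as proof of safety. That is something a reader of the report might infer, which is why the SAP should rule it out. The point warrants a change to the SAP but does not touch the trial's mechanistic objective.

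**What to change.** Keep the mixed models as supportive. Add to SAP 5.5 and 5.6, for every panel parameter, by treatment taken and period:

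1. The largest individual change from the period baseline (Visit 2 to 3, Visit 4 to 5), with a per-subject line plot. This is needed because a large fall that stays within range would not appear in item 2.
2. Shift tables (low, normal, high by the laboratory's reference range) and a listing of values outside range after a within-range baseline.
3. An adverse-event summary, on a safety set defined in SAP section 4.

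State that non-significant mean contrasts are not evidence of laboratory safety.

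The cost is SAP wording and a few tables from data already collected, with no added subjects, visits or samples. It assumes that the laboratory can supply its reference ranges, which the documents do not say. With 14 parameters, two periods and 20 subjects there are 14 × 2 × 20 = 560 post-challenge values. Some will fall out of range by chance, so the outputs should be read descriptively. They also cannot show that a rare harm is absent: at an assumed 5% risk per subject, the chance of at least one case among 20 is 1 − 0.95²⁰ = 64%.

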### 5.6 Secondary Efficacy Outcome Variables

Secondary Efficacy outcome variables: Erythrocytes, Haematocrit, Haemoglobin, INR. All variables are analysed like the secondary safety outcome variable analysis.

### 5.7 Sensitivity analysis on secondary variables

Percent change from baseline on the above secondary variables will also be analysed, where baseline value prior each period (visit 2 and visit 4) is set to index=100.

Subject 1, visit 2 = 1.2 (index=100)

Subject 1, visit 3 = 3.4 (index=283.3, calculated as  $100*3.4/1.2$ )

Subject 1, visit 4 = 2.3 (index=100)

Subject 1, visit 5 = 1.0 (index=43.5, calculated as  $100*1.0/2.3$ )

### 5.8 Data structure prior primary and secondary analysis

Below is the required data structure for using the statistical models (A and B are the two treatment groups).

subject	sequence	period	tmt	result	baseline
1 AB		1 A		3	0
1 AB		2 B		5	1
2 AB		1 B		4	4
2 AB		2 A		5	3
3 AB		1 B		4	0
3 AB		2 A		3	0
4 AB		1 B		0	2
4 AB		2 A		3	0
5 AB		1 A		4	0
5 AB		2 B		1	0
6 BA		1 A		3	0
6 BA		2 B		4	1
7 BA		1 B		3	0
7 BA		2 A		2	0
8 BA		1 B		4	0
8 BA		2 A		4	0
9 BA		1 A		1	1
9 BA		2 B		2	0
10 BA		1 A		2	1
10 BA		2 B		4	2

## 5.9 Challenge analysis

The challenge model will be analysed comparing baseline (visit 2 and 4) with “after” results (visit 3 and visit 5) using similar model as the primary and secondary outcome analysis with the following terms in the model:

- Treatment (Bif195 or Placebo)
- Sequence (first Bif195 or Placebo)
- Period (1 and 2)
- Before\_after (baseline and “after”)

The challenge model will thereby be analysed adjusted for period, sequence and treatment.

The data will be structured as seen below:

subject	sequence	period	tmt	Before_after	result
1 AB		1 A		before	1
1 AB		1 A		after	2
1 AB		2 B		before	1
1 AB		2 B		after	0
2 AB		1 B		before	4
2 AB		1 B		after	5
2 AB		2 A		before	4
2 AB		2 A		after	5
3 AB		1 B		before	4
3 AB		1 B		after	3
3 AB		2 A		before	4
3 AB		2 A		after	3
4 AB		1 B		before	0
4 AB		1 B		after	3
4 AB		2 A		before	0
4 AB		2 A		after	3
5 AB		1 A		before	4
5 AB		1 A		after	1
5 AB		2 B		before	4
5 AB		2 B		after	1
6 BA		1 A		before	3
6 BA		1 A		after	4
6 BA		2 B		before	3
6 BA		2 B		after	4
7 BA		1 B		before	3
7 BA		1 B		after	2
7 BA		2 A		before	3
7 BA		2 A		after	2

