## 4 Trial Population

For the statistical analysis, the randomized subjects will be divided into the following datasets:

Full Analysis Set (FAS):	Subjects who are randomized and have consumed at least one dose of study product and for whom efficacy data is available.
No response to challenge (NC)	Subjects not responding on the Aspirin challenge response defined as having Lanza score=0 on all visits (visits 2, 3 4 and 5)
Modified FAS (mFAS)	FAS population minus NC population.
Per Protocol Set (PPS)	Subjects, who are randomized and have consumed at least one dose of study product, have available efficacy data and have no major protocol deviations

All endpoints will be analyzed on the FAS populations. For sensitivity analysis, selected analyses will also be performed on the mFAS and PPS.

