## 5 Statistical Methodology

### 5.1 General statistical considerations

All statistical tests will be assessed using a nominal two-sided significance level of 5%.

The two treatment groups will be labelled as Bif195 and Placebo.

Weeks will be calculated as number of days divided by 7

Months will be calculated as number of days divided by 30.4375

Years will be calculated as number of days divided by 365.25

Number of days will be calculated using end date minus start date +1.

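### The blood-parameter challenge analysis (SAP 5.9) has four records per subject but only a patient random effect, so the coverage of its before/after test is not assured

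*SAP*

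**What the plan says.** SAP 5.9 compares visits 2 and 4 (before) with visits 3 and 5 (after). Its layout has four rows per subject and its fixed terms are treatment, sequence, period and Before_after: "The challenge model will thereby be analysed adjusted for period, sequence and treatment". The model is otherwise described only as "using similar model as the primary and secondary outcome analysis with the following terms in the model".

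For the blood safety parameters the model being borrowed is in SAP 5.5: "Each parameter will be analysed using a proc mixed model with patient as Random effect". SAP 5.6 extends it to erythrocytes, haematocrit, haemoglobin and INR: "All variables are analysed like the secondary safety outcome variable analysis". The table in SAP 1.2 repeats it. SAP 5.8 shows that this model was written for two rows per subject, one result per period with baseline as a covariate.

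No section names a patient-by-period term, a patient-by-Before_after term, a repeated-measures covariance, a robust variance or a degrees-of-freedom method. Tests are two-sided at 5% (SAP 5.1), with no multiplicity adjustment (SAP 5.11).

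**The concern.** With two rows per subject, one per period, a patient intercept is enough to describe the within-subject correlation. With four rows the layout is crossed: each subject has two periods and, in each, a before and an after value. A patient intercept alone says that all four values are equally correlated. Two ordinary features would break that.

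- **Change that differs between subjects.** If some people's values move more under aspirin than others', a subject's two changes are correlated. The before/after effect should then be judged against between-subject variation in change. The pooled residual is too small for this, and p-values come out too small.
- **Periods that differ within a subject.** The two visits of a pair are about 31 days apart, and the pairs are separated by a 6-week wash-out (Protocol 6.2, flow chart). Values within a period may be more alike than values across periods. That variation enters the pooled residual but cancels from the before/after contrast, so p-values come out too large.

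At stake is whether the stated confidence intervals and p-values can be relied on when the challenge analysis is used to say that aspirin did or did not move a blood parameter. The balance of the two features may differ between the 14 parameters, so a reader could not correct for it afterwards.

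**Working it through.** **The plan's own figure.** The documents give no figure for the challenge analysis. The trial's only power figure (Protocol 6.9.8) is for gene expression: 0.95 with 20 completers, coefficient of variation 0.344, 1.5-fold change. On the log scale with 20 per condition, ln(1.5) / (0.344 × √(2/20)) − 1.96 = 3.73 − 1.96 = 1.77, which gives power 0.96. The figure reproduces but has no bearing on this point, except to supply N = 20.

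**Inputs.** From the documents: N = 20, four records per subject, two-sided 5%, patient as the only random term. Assumed: residual variance Ve = 1, subject-by-period variance Vp, and subject-by-before/after variance Vb, varied over a range.

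**Correct variance.** Let D = ½[(V3 − V2) + (V5 − V4)] for each subject. Patient and period effects cancel, so Var(D) = Ve + 2Vb. The before/after estimate is the mean of D, with variance (Ve + 2Vb)/N and N − 1 = 19 degrees of freedom.

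**Variance used by the patient-only model.** Each subject has three within-subject contrasts, with variances Ve + 2Vb (before/after), Ve + 2Vp (period) and Ve (interaction). The model pools them, giving approximately [Ve + (2/3)(Vp + Vb)]/N on 4N − N − 3 = 57 degrees of freedom.

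**When the two agree.** Setting 2Vb = (2/3)(Vp + Vb) gives Vp = 2Vb. So they agree if Vp = Vb = 0 (equal correlation), or by coincidence if Vp is about twice Vb.

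**Worked cases.**
- Vb = 1, Vp = 0: correct 1 + 2 = 3, model 1 + 2/3 = 1.67, ratio 1.80. A correct p of 0.05 (t = 2.093 on 19 df) becomes t = 2.093 × √1.80 = 2.81 on 57 df, printed as p ≈ 0.007.
- Vb = 0, Vp = 1: correct 1, model 1.67, ratio 0.60. The same result becomes t = 2.093 × √0.60 = 1.62, printed as p ≈ 0.11.

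**Simulated type I error** (null true, complete balanced data, 20,000 trials per setting, N = 20):

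| Vp | Vb | Correlation of a subject's two changes, Vb/(Vb + Ve) | Patient-only model | t test on mean change |
|---|---|---|---|---|
| 0 | 0 | 0 | 5.0% | 5.1% |
| 0 | 0.25 | 0.20 | 8.4% | 5.0% |
| 0 | 0.5 | 0.33 | 11.0% | 4.9% |
| 0 | 1 | 0.50 | 14.3% | 5.1% |
| 1 | 0 | 0 | 1.3% | 4.9% |
| 1 | 0.5 | 0.33 | 5.5% | 5.2% |
| 1 | 1 | 0.50 | 8.8% | 5.2% |

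Repeat simulations agreed to within about 0.7 percentage points; the setting with Vp = 1 alone ranged from 1.2% to 1.6%. With 25 subjects the pattern is the same. As Vb grows without limit the variance ratio tends to 3 and type I error to about 26%; as Vp grows, type I error tends to zero.

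**Lanza.** In a small check on continuous data (200 replicates), a GEE clustered on patient with robust errors gave 5.5% to 6.5%.

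**The case against.** The strongest reply is that nothing here is shown to be wrong. If the four visits are equally correlated the planned test is exact, and the two departures pull in opposite directions: with Vp = 1 and Vb = 0.5 they nearly cancel. The documents give no variance components for any blood parameter. This stands in full. A reader might infer that the challenge p-values are too small, or that the intervals definitely lack their stated coverage. The documents support neither.

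A reader might also take the non-responder set in SAP 4 as the plan's own admission that response differs between subjects. That set is "Subjects not responding on the Aspirin challenge response defined as having Lanza score=0 on all visits". It is an endoscopic definition, and it says nothing about whether haemoglobin, INR or sodium respond differently from one subject to the next.

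The wording also leaves room for a richer covariance, since SAP 5.9 asks only for a similar model and lists only fixed terms. That stands in part: nothing forbids such a structure, but none is specified, and patient is the only random term written down. SAP 5.5 also falls back on non-parametric methods if normality fails on the raw and log2 scales, so the point applies only to parameters that stay in the mixed model.

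Finally, the analysis is supportive. SAP 5.9 names no blood parameter, the challenge analysis is not in the SAP 1.2 table or among the objectives, and the protocol calls all its endpoints exploratory. This limits the importance of the point but does not remove it.

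**Conclusion.** The point holds conditionally. As plainly read, the SAP tests the before/after effect in the blood parameters against a pooled residual that is right only under equal correlation or a coincidental balance of two variances. With pairs of visits separated by a wash-out, neither can be taken for granted. Coverage is therefore not assured, and the documents do not allow the direction or size of the error to be stated.

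The range from just over 1% to about 14% rests on assumed components (residual variance 1, the others 0 to 1), 20 complete subjects and normal data. It includes settings at or near the nominal 5%.

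The Bif195-versus-placebo comparison, which uses the two-record layout, is not affected. A Lanza GEE with robust errors is largely unaffected. This is a worthwhile improvement to a supportive analysis, not a threat to the trial's conclusions.

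**What to change.** In SAP 5.9, for parameters analysed by the mixed model, state that Before_after is tested against between-subject variation in change. Either form will do:

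- average (V3 − V2) and (V5 − V4) for each subject and test that mean, with one value per subject; or
- keep the four-row model and add random patient-by-Before_after and patient-by-period terms.

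The two agree only for complete balanced data with no variance estimate held at zero. If there is truly no variation in response and the estimate is bounded at zero, the second form, using 19 degrees of freedom, runs at about 3.8%, slightly conservative. About 20% drop-out is expected (Protocol 6.9.8) and nothing is imputed (SAP 5.3), so the SAP should also say how a subject with a single before/after pair enters. The mixed-model form is preferable for those subjects. Name the degrees-of-freedom method too.

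The cost is one derived variable or two RANDOM terms in SAS, with no new data. Denominator degrees of freedom fall from about 57 to about 19. The critical value rises from 2.00 to 2.09, so intervals would be about 5% wider (2.093/2.002 = 1.045) if equal correlation did hold.
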